3.1. Part 1 Safety Run-In Portion

The safety run-in portion was designed to test up to 3 doses of INC050465 in combination with ruxolitinib for a 28-day assessment (4 weeks). Initially, 3 participants were to be enrolled in Cohort 1 to receive INC050465 10 mg together with ruxolitinib, at the dose ongoing at the time of enrollment. After 28 days, participants who took at least 22 of 28 daily doses of INC050465 AND ruxolitinib OR had a DLT during the first 28 days (refer to Table 3 of the Protocol) were to

be included in the evaluation cohort. Additional participants were to be enrolled into Cohort 1 if discontinuations result in fewer than 3 evaluable participants. After evaluation, the actions listed in [Table 1](#) would occur.

Table 1: Safety Run-In Cohorts

Cohort	No. of Participants	Regimen	DLTs Observed	Action Taken
1	3	INCB050465 10 mg QD for 8 weeks, followed by 10 mg once weekly plus ruxolitinib at 5 mg BID to 25 mg BID ^a	0	Proceed to Cohort 2.
			1	Enroll 3 additional participants, and evaluate the total of 6 participants after 28 days. If < 2 participants have a DLT, then proceed to Cohort 2. If ≥ 2 participants have a DLT, proceed to Cohort 3.
			> 1	Proceed to Cohort 3.
2	3	INCB050465 20 mg QD for 8 weeks, followed by 20 mg once weekly plus ruxolitinib 5 mg BID to 25 mg BID ^a	0 or 1	Enroll 3 additional participants, and evaluate the total of 6 participants after 28 days. If < 2 participants have a DLT, then proceed to Part 2 using doses of 10 mg and 20 mg of INCB050465.
			≥ 2	Proceed to Cohort 3.
3	6	INCB050465 5 mg QD for 8 weeks, followed by 5 mg once weekly plus ruxolitinib 5 mg BID to 25 mg BID ^a	0 or 1	If < 2 participants have a DLT and if Cohorts 1 and 2 exceeded DLT allowance, then proceed to Part 2 as a single arm study of 5 mg of INCB050465. If Cohort 1 did not exceed DLT allowance, proceed to Part 2 with doses of 5 mg and 10 mg INCB050465.
			≥ 2	Terminate study. Alternatively, sponsor may elect to assess doses lower than 5 mg.

^a The dose of ruxolitinib will be that which the participants had been taking for at least 8 weeks before the first dose of INCB050465. The maximum dose of ruxolitinib allowed for participants with baseline platelet count $\geq 100 \times 10^9/L$ is 25 mg BID, and the maximum dose of ruxolitinib for participants with baseline platelet count of $\geq 50 \times 10^9/L$ to $< 100 \times 10^9/L$ is 10 mg BID.

3.2. Part 2 Randomized Portion

The open-label randomized portion of the study was planned to enroll approximately 60 participants randomized 1:1 by block randomization into 2 treatment groups, TG10 and TG20.

Enrollment into Part 2 at a given study site was terminated effective with site-specific IRB approval of Protocol Amendment 5.

3.3. Part 3 Randomized Portion

In Part 3, all participants were planned to initially receive INCB050465 at 20 mg QD for 8 weeks in combination with ruxolitinib. After Week 8, participants were to be assigned to 1 of 2 dose groups based on block randomization at the time of entry into the study (using a randomization of 3:2 for TG5 vs TG20 for the first 40 participants, followed by 1:1 randomization for additional participants, up to a total of approximately 52 participants).

Enrollment in Part 3 was suspended with implementation of Amendment 6. Participants already enrolled into TG5 in Part 3 would continue to receive INCB050465 according to the original randomization for Part 3 and may continue in the study indefinitely unless criteria for discontinuation are met. Participants already enrolled into TG20 in Part 3 would have the opportunity to cross over to receive INCB050465 5 mg QD once they reach Week 8 provided they demonstrate inadequate response to the current dose regimen.

3.4. Part 4 Randomized Portion

During Part 4, participants will be randomized on a 3:2 ratio between TG5D and TG5I/M until 25 total participants have been randomized, with subsequent randomization on a 1:1 ratio until approximately 30 participants have been enrolled in each group. Stratification will be by ECOG status as in Part 3.

3.5. Crossover Portion

With IRB approval of Protocol Amendment 5 at a given site, participants randomized to TG10 in Part 2 at that site may cross over to either 20 mg QD followed by 5 mg QD after Week 8 (if participant is within the first 8 weeks of treatment at the time of crossover), or to 5 mg QD (if participant is beyond 8 weeks of treatment and receiving 10 mg once weekly at the time of crossover). With IRB approval of Protocol Amendment 6 at a given site, participants randomized to TG20 at that site may cross over to 5 mg QD once Week 8 has been reached. All potential crossover participants must meet the criteria listed in Protocol Amendment 6, Section 5.2.3.

Participants who do not meet these criteria, or participants who do meet the criteria but do not wish to cross over, may continue on the originally assigned regimen, and may crossover at any time provided the criteria for crossover are met and crossover is determined by participant and investigator to represent the best option.

The crossover portion starts when the participants are assigned to and receive their first dose of a different treatment. The original portion of the study for crossover participants ends the day before crossover.

3.6. Control of Type I Error

For the primary endpoint in Parts 2, 3, and 4, the overall 2-sided Type I error is 0.10 for detecting a difference between TG5D and TG5 (TG5I/M). This means that there is a 10% risk of observing a significant location shift in percentage change of spleen volume from baseline between TG5D and TG5 (TG5I/M) even when there is none.

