### 1.8.3. Potential Benefits of INCB050465 Based on Prior and Ongoing Clinical Studies

Based on emerging efficacy and safety data from the ongoing Study INCB 50465-101 (see Section 1.5.4.1), the treatment regimen for Study INCB 50465-201 Part 1 was selected to be 10 mg QD (Cohort 1) or 20 mg QD (Cohort 2) given for 8 weeks, followed by 10 mg (Cohort 1) or 20 mg (Cohort 2) given once weekly. Doses of 10 mg or 20 mg QD provide trough concentrations exceeding the IC90 (based on an *in vitro* whole-blood assay). Furthermore, 20 mg QD has demonstrated efficacy in DLBCL and in other types of NHLs. However, 24% of all subjects in study INCB 50465-101 discontinued study treatment due to an AE. Consequently, after administration of daily INCB050465 for 8 weeks in the present study, the dosing regimen was reduced to once-weekly dosing for Part 1 and Part 2.

Pharmacodynamic data from INCB 50465-101 showed that a single dose of 20 mg exhibited maximal inhibition of AKT in an *ex vivo* pharmacodynamic assay, and PK modeling suggests that 20 mg once weekly will 1) achieve maximal inhibition equivalent to approximately  $10 \times$  IC90, 2) exceed the IC90 for approximately 36 hours, and 3) have minimal to no inhibition for approximately half the dosing interval. This once-weekly regimen is similar to that of another PI3K inhibitor (copanlisib), which is administered IV on Days 1, 8, and 15 of a 28-day cycle, and which achieved 7 objective responses in 9 subjects with NHL ([Patnaik et al 2016](#)). Among the 51 subjects who received study drug, 4 discontinued treatment due to an AE. There were 2 events of Grade 3 noninfectious pneumonitis, 1 event of Grade 3 diarrhea, and no events of colitis.

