### **9.3. Level of Significance**

The level of significance for detecting a difference between TG5D and TG5I/M + TG5 for the primary endpoint is 10% (2-sided). In other words, there is a 10% risk of declaring a difference in the percentage change in spleen volume between the 2 groups when it is not so.

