3.7.2. Sample Size in Randomized Portion

The sample size and power calculations for the randomized portion of the study are based on a 2-sample Wilcoxon rank sum test with a normal approximation applied to the test statistic. The data from Study INCB 18424-351 (COMFORT-1) suggested a mean reduction of 8.44 in percentage change from baseline of spleen volume with a standard deviation of 14.5 from baseline to Week 12 for the active group in that study. For a 2-sided Type I error of 0.10 and Type II error of 0.10 with 30 participants per treatment group, the test is powered to detect an 11.4 percentage point location shift between the 2 groups in regards to percentage change in spleen volume. The 2 populations are assumed to be normally distributed with a common standard deviation of 14.5.

In the event that only 1 dose was selected during the Part 1 safety-run in portion of the study or the event that 1 of the treatment groups was terminated for futility at the interim analysis during the randomized portion, the median spleen volume reduction would be estimated and a CI constructed based on the exact binomial CI. [Figure 4](#) plots the power of the design with 30 participants per treatment group at various percentage point location shifts between the 2 groups in spleen volume reduction.

Figure 4: Plot of Power at Various Differences Between Treatment Groups

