7.3. Analysis of the Primary Efficacy Parameter

7.3.1. Primary Efficacy Analysis

The primary endpoint is change and percentage change in spleen volume from baseline at 12 weeks as measured by MRI (or CT scan in applicable participants). A location shift in percentage change in spleen volume between TG5D and TG5I/M for stratification by ECOG performance status at screening (0 or 1 vs 2) will be assessed using a van Elteren test ([van Elteren 1960](#)).

The baseline spleen volume will be measured by MRI (or by CT for applicable participants) during the baseline visit (Days -7 to 1); the last value will be used if there are multiple values measured during the baseline visit.

The Week 12 spleen volume will be measured by MRI (or by CT for applicable participants) during the Week 12 visit (Day 84 ± 7 days); the last value will be used if there are multiple values measured during the Week 12 visit.

Within each stratum, participants who discontinue from the study or who have missing values for the Week 12 spleen volume will be imputed as having the largest possible percentage increase in spleen volume and given the lowest rank in the stratum. The participant with the largest percentage reduction in spleen volume in a stratum will be given the highest rank within the stratum. In the case of ties, average ranks will be assigned.

If the study fails to enroll a sufficient number of participants in a particular stratum, a sensitivity analysis using a 2-sample Wilcoxon rank sum test with a normal approximation applied to the test statistic, for purposes of calculation stability, will be conducted. Ranking will be carried out using the same approach but without stratification.

Results for participants enrolled to TG10 or TG20 will be summarized descriptively with no formal statistical comparisons performed.

Statistical comparison will be conducted for TG5D versus TG5 (TG5I/M). To explore the difference in daily dosing and daily/weekly dosing, the statistical comparison will also be performed for daily dosing (TG5D + TG5I/M) versus daily/weekly dosing (TG10 + TG20).

In the event of a single-arm trial, a 95% CI for median percentage change in spleen volume from baseline at Week 12 will be calculated from the exact binomial distribution.

The percentage change from baseline at Week 12 will be calculated using the formula:

$$\% \text{ change} = 100 \times [\text{Week 12 spleen volume} - \text{baseline spleen volume}] / \text{baseline spleen volume}$$

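### The stated 10% false-positive risk for spleen volume holds only if missing Week 12 scans are equally common in both arms

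*SAP*

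**What the plan says.** SAP 3.6 explains the two-sided 0.10 level for TG5D against TG5 (TG5I/M) by saying that "there is a 10% risk of observing a significant location shift in percentage change of spleen volume" even when there is none. Protocol 9.3 puts it as "there is a 10% risk of declaring a difference in the percentage change in spleen volume between the 2 groups when it is not so". SAP 7.2.1 words the primary hypothesis as a shift in Week 12 percentage change in spleen volume, without mentioning discontinuation.

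SAP 7.3.1 and Protocol 9.4.1.1 specify a van Elteren test stratified by ECOG status. A participant who discontinues the study or has no Week 12 volume is treated as having the largest possible increase and is "given the lowest rank in the stratum". Ties take average ranks. The only sensitivity analysis named in SAP 7.3.1 is an unstratified Wilcoxon test for a sparse stratum, and it keeps the same ranking.

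The sample size (SAP 3.7.2, Protocol 9.2) assumes normal data and makes no allowance for missing scans.

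**The concern.** The sentence about the 10% and the ranking rule describe different null hypotheses. The sentence concerns spleen volume alone. The rule makes the ranked outcome a composite in which early loss or a missing scan comes last and spleen change orders everyone else. If the arms have the same spleen response but lose different numbers before Week 12, the composite differs. The test then rejects more than 10% of the time, and the plan's wording would report a spleen-volume shift.

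This matters because the arms differ in exactly the period that feeds the endpoint: 20 mg daily against 5 mg daily for the first 8 of 12 weeks. After treatment stops, Protocol 5.6.2 describes an end-of-treatment visit and then phone contact about every 12 weeks, while Protocol 7.6.3 ties scans to scheduled weeks. A participant who stops early may therefore have no Week 12 volume, whatever the spleen did. A tolerability difference could be read as a spleen difference.

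**Working it through.** **Inputs.**
- From SAP 3.7.2: a two-sided level of 0.10, planned power 0.90 and 30 per arm, for which "the test is powered to detect an 11.4 percentage point location shift between the 2 groups". Outcomes are taken as normal, with the same SD of 14.5 in each arm.
- The null simulation centres both arms on the prior-study mean, where the data "suggested a mean reduction of 8.44 in percentage change from baseline of spleen volume with a standard deviation of 14.5". A rank test does not depend on this centre.
- Missingness before Week 12 is not stated for this trial. It is assumed, and shown as a range.

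**Step 1: reproduce the plan's figure.** Simulating the rank-sum test with complete data (100,000 trials, 30 per group, shift 11.4, SD 14.5, two-sided 0.10) gives power 0.900, as stated. With no shift the rejection rate is 0.099. The sample size and the 10% are both right for complete data.

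**Step 2: what worst-ranking does under equal spleen change.** Let a and b be the missingness probabilities in the two arms. The probability that a random participant from the first arm outranks one from the second, counting ties as half, is

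(1−a)(1−b)/2 + ab/2 + (1−a)b = 0.5 + (b−a)/2.

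It is 0.5 only when a = b. With 10% vs 20% it is 0.55, although the spleens behave identically.

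**Step 3: approximate rejection rate.** With n per arm, the rank-sum count moves by n²(b−a)/2. Its SD is about √(n²(2n+1)/12), ignoring the small tie correction. For n = 30 the SD is √(900×61/12) = 67.6.
- 10% vs 15%: 22.5/67.6 = 0.333. Φ(−1.645+0.333) + Φ(−1.645−0.333) = 0.095 + 0.024 = 0.119.
- 10% vs 20%: 45/67.6 = 0.665. Φ(−0.980) + Φ(−2.310) = 0.164 + 0.010 = 0.174.
- 10% vs 30%: 90/67.6 = 1.331. Φ(−0.314) + Φ(−2.976) = 0.377 + 0.001 = 0.378.

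For n = 15 the SD is √(225×31/12) = 24.1. At 10% vs 20%, 11.25/24.1 = 0.467, which gives Φ(−1.178) + Φ(−2.112) = 0.119 + 0.017 = 0.137.

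**Step 4: simulation.** There were 60,000 trials per row, with independent missingness, average ranks for ties and tie-corrected variance. The van Elteren column assumes an 80/20 split between ECOG strata. A dash means not run.

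| Missing, arm 1 vs arm 2 | Rank-sum, 30 per group | Van Elteren, 30 per group | Rank-sum, 15 per group |
|---|---|---|---|
| 0% vs 0% | 9.9% | 9.8% | – |
| 10% vs 10% | 10.0% | – | – |
| 20% vs 20% | 10.1% | 10.1% | – |
| 30% vs 30% | 9.8% | – | – |
| 10% vs 15% | 11.8% | – | – |
| 10% vs 20% | 17.3% | 17.5% | 13.7% |
| 10% vs 25% | 26.4% | 26.1% | – |
| 10% vs 30% | 38.5% | 38.2% | 24.8% |

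The hand calculation and the simulation agree. The gap between arms drives the result; the overall level of missingness does not.

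**Step 5: what else is planned.**
- SAP Appendix A lists percent change in spleen volume by visit and group (Table 2.1.1.1) and disposition (Table 1.1.2.1, with reasons under SAP 6.2).
- SAP 7.3.1 adds an ECOG-stratified Cochran-Mantel-Haenszel test on reduction categories with no imputation rule of its own. Under the default in SAP 4.1.6 it may use observed scans only, but the plan does not say so.
- None of these is a rank test on observed percentage change, a between-arm shift estimate, or a count of participants worst-ranked at Week 12.

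**The case against.** **The rule is legitimate and disclosed.** Ranking early loss as the worst outcome is a recognised choice, prespecified in both documents. If the regimens do not differ in loss or spleen effect, the 10% is correct. This stands. The fault lies in what the 10% and the hypothesis are said to refer to, and the test need not change.

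**A reader might infer that the false-positive rate in this trial is in fact inflated.** The documents do not show that. They give no missingness by arm. Protocol 1.8.3 reports that "24% of all subjects in study INCB 50465-101 discontinued study treatment due to an AE", and Protocol 1.5.4 gives 19.0% to 19.4% for other studies or data cuts. These are AE discontinuations over whole treatment in other diseases, not missing scans by Week 12, and none is a difference between arms. They show no evident dose gradient either: 19.2% at 0.3 to 10 mg daily with itacitinib, and 19.0% on a regimen starting at 20 mg daily, though the populations differ. Part 1 saw no DLTs, and Protocol 1.8.3 calls safety similar between dose groups. That last statement predates any 5 mg-from-Day-1 group, so it does not settle the comparison, but it gives no support for a large gap.

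**A reader might also infer that loss and spleen effect cannot be told apart at all.** That goes too far. The by-visit summaries, disposition by reason and the categorical test give partial information.

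**Size.** A 5-point gap adds only about 2 points. SAP 5.2 and 10.2.3 say the study and its enrollment ended early, and smaller groups make the inflation smaller.

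**Conclusion.** The point holds in conditional form. The 10% in SAP 3.6 and Protocol 9.3 is the error rate for the joint null of equal spleen change and equal missingness, not for spleen volume alone as worded. Under equal spleen change and 30 per group, rejection stays near 10% with equal missingness and rises to about 12%, 17% and 38% for gaps of 5, 10 and 20 points above 10%. At 15 per group the 10-point gap gives about 14%. These figures rest on assumed, independent missingness and normal data with SD 14.5. They illustrate sensitivity and do not estimate what happened. This should be fixed because it changes what a significant primary result can be said to show. It does not invalidate the primary test.

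**What to change.** 1. Reword SAP 3.6, SAP 7.2.1 and Protocol 9.3 so that the 10% and the hypothesis refer to the composite rank outcome: early loss or missing Week 12 scan ranked worst, then spleen change.
2. Keep the primary test. Add to SAP 7.3.1 a supportive van Elteren test in participants with both baseline and Week 12 volumes, with a Hodges-Lehmann shift and a 90% CI to match the two-sided 10% level. State its downside: it may be biased if loss is related to spleen response.
3. Report the number worst-ranked at Week 12 by arm and reason.
4. Describe a significant primary result as a composite difference, and interpret it beside the observed-scan estimate and CI.

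A rule that claims a spleen effect only when the observed-scan estimate points the same way is not a substitute. In 20,000 simulated trials at 30 per group it lowered false conclusions only from 17.6% to 16.9% (10% vs 20%) and from 38.1% to 31.0% (10% vs 30%).

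The cost is a few sentences, one more run of the same test with an estimate, and one small table. No new data are needed. The claim that a significant result supports becomes somewhat narrower.

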3.7. Sample Size Considerations

3.7.1. Cohort Size in Safety Run-In Portion

For the safety run-in portion, the decision to de-escalate the dose was driven by the number of observed toxicities and could be calculated based on the binomial distribution. During the safety run-in portion of the study, dose escalation between Cohorts 1 and 2 was to follow a 3 + 3 design algorithm. Doses were to be selected for Part 2 based on the safety outcomes in the Part 1 safety

run-in portion of the study, according to the rules outlined in [Table 2](#). In the table, a cohort is considered toxic if 2 or more of the first 6 participants experienced a DLT. A cohort is considered safe if fewer than 2 of the first 6 participants experienced a DLT with the exception that Cohort 1 will also be considered safe for escalating to Cohort 2 if 0 of the first 3 participants experience a DLT. There was alternative allowance to assess additional doses if Cohort 3 was determined to be above the MTD.

Table 2: Matrix of Part 2 Dose Selection Based on Part 1 Safety Outcomes by Dose Cohort

Cohort 1 10 mg QD	Cohort 2 20 mg QD	Cohort 3 5 mg QD	Decision for Part 2
Toxic	Toxic	Safe	Single arm or explore dose < 5 mg QD
Safe	Toxic	Safe	Randomized between 5 mg QD and 10 mg QD
Safe	Safe		Randomized between 10 mg and 20 mg QD
Toxic	Toxic	Toxic	Terminate or explore doses < 5 mg

During Part 1, the probabilities of declaring a dose to be tolerable for the 3 cohorts at various DLT rates are provided in [Table 3](#).

Table 3: Probability of Declaring a Dose to be Tolerable

[figure not shown]
True DLT Rate	Probability of Declaring the Dose to be Tolerable	
	In Cohort 1	In Cohorts 2 and 3
20%	70.8%	65.7%
30%	49.4%	42.0%
40%	30.9%	23.3%
50%	17.2%	10.9%
60%	8.02%	4.01%

3.7.2. Sample Size in Randomized Portion

The sample size and power calculations for the randomized portion of the study are based on a 2-sample Wilcoxon rank sum test with a normal approximation applied to the test statistic. The data from Study INCB 18424-351 (COMFORT-1) suggested a mean reduction of 8.44 in percentage change from baseline of spleen volume with a standard deviation of 14.5 from baseline to Week 12 for the active group in that study. For a 2-sided Type I error of 0.10 and Type II error of 0.10 with 30 participants per treatment group, the test is powered to detect an 11.4 percentage point location shift between the 2 groups in regards to percentage change in spleen volume. The 2 populations are assumed to be normally distributed with a common standard deviation of 14.5.

In the event that only 1 dose was selected during the Part 1 safety-run in portion of the study or the event that 1 of the treatment groups was terminated for futility at the interim analysis during the randomized portion, the median spleen volume reduction would be estimated and a CI constructed based on the exact binomial CI. [Figure 4](#) plots the power of the design with 30 participants per treatment group at various percentage point location shifts between the 2 groups in spleen volume reduction.

Figure 4: Plot of Power at Various Differences Between Treatment Groups

3.8. Schedule of Assessments

Refer to Protocol Amendment 6 dated 11 OCT 2018 for a full description of all study procedures and assessment schedules for this study.

4. DATA HANDLING DEFINITIONS AND CONVENTIONS

4.1. Scheduled Study Evaluations and Study Periods

4.1.1. Day 1

Day 1 is the date that the first dose of study drug INCB050465 is administered to the participants. For randomized participants not treated with any study drug, Day 1 is defined as the day of randomization.

